with event-related potentials (ERPs), and will be performed as described previously. Baseline normalized evoked/Induced power and Interelectrode Coherence (ITC; also termed phase locking factor) will be determined using a wavelet-based time-frequency spectrogram via Analyzer 2.0. EEG Source Analysis: Standardized Low Resolution Brain Electromagnetic Tomography (sLORETA): Based on the scalp-recorded electric potential distribution, standardized low resolution brain electromagnetic tomography (sLORETA) will be used to compute the cortical three-dimensional distribution of current density. This will allow us to examine mGluR5 availability in ROIs in relation to EEG sources. The particular form of standardization used in sLORETA endows the tomography with the property of exact localization to test point sources, yielding images of standardized current density with exact localization, albeit with low spatial resolution (i.e. neighboring neuronal sources will be highly correlated). 104,105 sLORETA is the method of choice since it has no localization bias even in the presence of measurement and biological noise. 104 Furthermore, sLORETA has been validated in several simultaneous EEG/fMRI studies,  and in an EEG localization study for epilepsy.  In the current implementation of sLORETA, computations will be made both in a realistic head model,  using the MNI152 template,  and using each subject's structural MRI, with the three-dimensional solution space restricted to cortical gray matter, as determined by the probabilistic Talairach atlas. The intracerebral volume is partitioned in 6239 voxels at 5 mm spatial resolution. C.2.d. EEG Paradigms: RAVLT Task: A modified computer version of the Rey Auditory Verbal Learning Test (RAVLT) similar to Babiloni et al. (2009) will be utilized. The RAVLT will be administered while EEG data are collected in three separate conditions. In the passive listening condition, subjects will passively listen to a list of 15 words (presented one at a time) six times in a row. In the memory encoding condition, subjects will be administered a list of 15 words played one at a time, five times, and will be told to try and remember the list and to repeat as many words as possible after each list. A sixth distractor list will also be administered after the primary list as in the standard RAVLT. The inclusion of separate passive listening (which is not part of the standard RAVLT) and memory/encoding conditions will be included in order to compare neural signatures for both basic linguistic processing and processes related to memory encoding. Twenty minutes after the end of the encoding phase, subjects will be asked to repeat as many words as they can from the original list of words (the free recall phase). EEG will not be collected during the free recall phase. Following free recall, subjects will engage in a computerized recognition condition of the RAVLT. Subjects will hear words from the (1) original memorized list, (2) the distractor list, and (3) novel words not heard that day. Subjects will respond with a three-choice button box to indicate from which list each word originated. Words in the recognition condition will be presented every 4 seconds. This EEG version of the RAVLT allows separate examinations of neural oscillations during passive listening, memory encoding, and recognition. In addition, the words will be post-hoc sorted based on correct performance to examine activity during encoding for words that were accurately recalled (the "subsequent memory effect"). LTP Task: We induce and measure LTP using EEG with repetitive sensory stimulation. 100 This paradigm has been shown to have the properties of LTP including (1) frequency dependency, (2) temporal stability, (3) input specificity, and (4) de-potentiation by low frequency stimulation.  Tone pips (tone frequency 1000 Hz, presented for 50 msec) will be used in all stages of the task (i.e., for baseline, tetanus, and post-tetanic recording). During the baseline recording, 120 tone pips will be

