#### Schema

#### Schedule of Activities (SoA)

OUTCOMES	SOURCE/MEASURE	нс	CUD (baseline) Day 0	CUD (abstinence) Day 28
Neural Recepto	ors			
mGluR5 Availability	PET ROI's $V_T$ : OFC, anterior cingulate, vmPFC, dlPFC, hippocampus, amygdala	X	X	X
Cannabis Use Disorder — Clinically Relevant Functional Measurements				
CUD Severity	DSM-5		X	
Cannabis Use Patterns	Timeline Follow Back		X	X
Cannabis Withdrawal Severity	Cannabis Withdrawal Scale		X	X
Cannabis Craving	7-point Scale		X	X
Cannabis- Related Problems	Marijuana Problems Scale		X	
Impulsivity	BIS/BAS	X	X	

Reward Processing	Probabilistic Reward Task	X	X	X
Mood	HAM-D, MADRS, Visual Analog Scale for Mood States	X	X	X
Sleep	Pittsburgh Sleep Quality Index	X	X	X
Cannabis Biomarkers				
Cannabis Use Status	Urinary THC-COOH*	X	X	X
Neural Function				
Verbal Memory	EEG: Theta band power/coherence	X	X	X
Synaptic Plasticity / LTP	EEG: N100-P200 amplitude increase after auditory tetanus	X	X	X
Neurocognitive Function	CogState Cognitive Battery	X	X	X

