On each of the scan days, CUD and controls subjects will also be administered neuropsychological tests from the CogState Cognitive Battery[123,124], which we previously showed to be sensitive to detecting cognitive deficits in mood disorders[125]: executive control (Groton Maze Learning task, GMLT; Set-Shifting task, SST and Go No-Go, GNG)[126-134] and working memory (One Back task, ONB, and Two Back task, TWB)[135-137]. Further, the battery has been well-validated (studies using CogState batteries have been published in over 100 peer-reviewed journals). Most important for the current study, this battery is ideal for within-subject designs (i.e., it was specifically developed for repeated administration with minimal practice or learning effects). Finally, the CogState has been shown to have high test-retest reliability, thorough coverage of cognitive domains, comparable alternative forms, strong internal consistency, is well established in the general population, and has proven tolerability and acceptability. The entire battery takes approximately 30 minutes. For mood assessment, the Hamilton Depression Rating Scale (HAM-D) and Montgomery-Asberg Depression Rating Scale (MADRS) will be administered by highly trained and reliable raters. These assessments will be administered at screening and at the time of PET scans.

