Aim 2: Within CUD subjects, to examine the associations between mGluR5 availability and: (a) CUD severity; (b) impulsivity; (c) EEG; and (d) neurocognition. Hypothesis 2: Higher mGluR5 availability will be associated with: (a) greater CUD severity (by DSM-5); (b) higher impulsivity; (c) lower theta-band power and LTP, and (d) worse performance on verbal memory. Power Calculations for Hypothesis 2: Using the same standards applied for hypothesis 1, we considered our preliminary data and conducted a literature review to determine what magnitude of correlation we could reasonably expect to see in this study between relevant variables of interest. We included studies with similar methodologies, which reported correlations between similar variables (i.e. similar EEG measures and cognitive/behavioral constructs, and an *in vivo* measurement of neuroreceptor or transporter availability in humans using PET). Examples include an unpublished study from our research group in which the correlation between mGluR5 availability and impulsivity in BPD and PTSD individuals ranged from 0.46. to 0.80 in frontal and limbic brain regions of interest (n= 56). Observed correlations ranged in magnitude from 0.21 to 0.80 (positive or negative) with a median r = 0.57. Magnitude of relevant correlations observed in our preliminary data are comparable (i.e., correlation between impulsivity and fronto-limbic mGluR5 availability, r = 0.896). We will evaluate aim 2 using correlational analyses. Using a correlation estimate of 0.55 (based on both review of the literature and our pilot data) and a two-tailed  $\alpha = 0.05$ , a priori power analysis suggested we will require a minimum n = 24 to achieve more than 80% power for the planned analysis. As we plan to conduct correlational analyses within the CUD group (n = 30), we will be adequately powered to test this hypothesis. Data Analysis for Hypothesis 2: Correlational analysis (Spearman or Pearson, as appropriate based on observed data distributions) will be used to test for associations between fronto-limbic mGluR5 availability, CUD severity, impulsivity,  $\theta$ - band power and LTP, and working memory performance. Multiple regression analyses will also be considered to control for potential confounding variables. a will be set at 0.05 for all planned correlational analyses. We will also assess for associations between mGluR5 availability and performance on

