other domains as secondary/exploratory analyses, keeping significance at the same level. Significant positive correlations between fronto-limbic mGluR5, CUD severity, and impulsivity will be supportive of Hypothesis 2. Likewise, significant negative correlations between fronto-limbic mGluR5, θ- band power and LTP, and working memory performance will be considered supportive of hypothesis 2. Of note, the relationship between other relevant and clinically meaningful variables pertaining to CUD (e.g. craving, withdrawal, duration/intensity of use), and mGluR5 availability will also be examined in exploratory analyses. The influence of potentially relevant demographic variables including **age and sex will be examined.** 

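### Hypothesis 2(d) predicts verbal memory but is tested and credited on working memory, and the LTP part of 3(b) has no listed model or success criterion

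*Combined protocol and SAP*

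**What the plan says.** **Hypothesis 2(d).** Hypothesis 2 appears four times: in the Synopsis (Specific Aims), 3.1, 9.1 and 9.2. Each time its last component is "d) worse performance on verbal memory". The data analysis paragraph for Hypothesis 2 in 9.2 then correlates the fronto-limbic composite with CUD severity, impulsivity, theta power, LTP and working memory. It closes by stating that a negative correlation with "working memory performance will be considered supportive of hypothesis 2". Remaining cognitive measures fall under "other domains as secondary/exploratory analyses, keeping significance at the same level".

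**Instruments.** Section 6.1.1 describes the CogState battery as "executive control (Groton Maze Learning task, GMLT; Set-Shifting task, SST and Go No-Go, GNG") and "working memory (One Back task, ONB, and Two Back task, TWB"). Verbal memory is tested by the RAVLT, described in the Synopsis under EEG Paradigms (C.2.d): "The RAVLT will be administered while EEG data are collected in three separate conditions". The Synopsis and 6.1.1 both call the EEG optional. In the Schedule of Activities, and again in 8.1, the measure in the Verbal Memory row is "EEG: Theta band power/coherence".

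**Hypothesis 3(b).** This predicts that theta power and LTP increase after abstinence (Synopsis, 3.1, 9.1, 9.2). Section 9.2 says Hypothesis 3 will be evaluated by repeated measures ANOVA and then lists three models: mGluR5 availability, theta power with coherence, and cognition. The success rule covers the same three. The LTP outcome, N100-P200 amplitude after versus before the tetanus, is defined under the LTP Task in the Synopsis and scheduled for CUD subjects at Day 0 and Day 28.

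Sections 9.4.1 to 9.4.3 only refer back to 9.2, and 9.4.9 (Exploratory Analyses) has no text.

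**The concern.** A hypothesis, its planned test and the rule for calling it supported should name the same outcome. Here they do not, in two places.

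For 2(d), a One Back or Two Back correlation would be reported as support for a prediction about verbal memory. A RAVLT result in either direction would not enter the rule. For 3(b), support could be claimed on theta power and coherence even if LTP stayed flat or fell.

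Every planned correlation in Aim 2 is tested at 0.05. A fixed link from each hypothesis to one outcome is therefore an important protection against choosing the outcome after the data are seen.

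**Working it through.** This is a question of wording, so the check sets the texts side by side. One figure bears on the remedy and is reproduced at the end.

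**1. Hypothesis against analysis**

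| Component | Hypothesis | Planned analysis in 9.2 | Success rule in 9.2 | Match |
|---|---|---|---|---|
| 2(a) | CUD severity | CUD severity | CUD severity | yes |
| 2(b) | impulsivity | impulsivity | impulsivity | yes |
| 2(c) | theta power | theta power | theta power | yes |
| 2(c) | LTP | LTP | LTP | yes |
| 2(d) | verbal memory | working memory | working memory | **no** |
| 3(a) | mGluR5 | model 1 | model 1 | yes |
| 3(b) | theta power | model 2 (with coherence) | model 2 | yes |
| 3(b) | LTP | none listed | none | **no** |
| 3(c) | memory | model 3, cognition | model 3 | broader term, no test named |

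Verbal memory is the 2(d) outcome in 4 of 4 statements of the hypothesis and in 0 of 2 statements of its analysis (the correlation and the success rule). In the Aim 3 text of 9.2, LTP appears in the hypothesis, in 0 of 3 listed models, and not in the rule. Because LTP is retained in the Aim 2 correlations, the omission is specific to Aim 3.

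**2. Could working memory stand for verbal memory?** Not on the plan's own description. The CogState tests listed cover executive control and working memory only. List learning, free recall and recognition belong to the RAVLT, which 9.2 never mentions. The schedule's Verbal Memory row does not help: it records theta power and coherence, which are EEG measures already covered by 2(c). Hypothesis 2(d) is about performance.

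**3. Is either gap filled elsewhere?** No. Sections 9.4.1 to 9.4.3 add nothing to 9.2, and 9.4.9 is empty.

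**4. Size.** Two of the seven lettered components are affected, 2(d) and 3(b). Counting theta and LTP separately, as in the table, gives 2 of 9 rows.

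**5. Sample size if the RAVLT becomes the test of 2(d).** Inputs from 9.2: r = 0.55, two-sided alpha 0.05, and "we will require a minimum n = 24 to achieve more than 80% power". By Fisher z, power = Φ(atanh(r) × √(n − 3) − 1.96), with atanh(0.55) = 0.618.

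- n = 24: 0.618 × √21 = 2.834; 2.834 − 1.96 = 0.874; power 0.809
- n = 23: 0.618 × √20 = 2.766; 2.766 − 1.96 = 0.806; power 0.790
- n = 30: 0.618 × √27 = 3.213; 3.213 − 1.96 = 1.253; power 0.895

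The plan's minimum of 24 is reproduced. A bivariate normal simulation gives slightly higher power (0.826 at n = 24, 0.808 at n = 23), so the threshold can move by one subject with the method. With 30 CUD subjects, 24/30 = 80% would need RAVLT data. The plan gives no expected EEG uptake.

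**The case against.** The case against accepts the wording and disputes its weight.

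- **The success rule is descriptive.** The text says which results would be supportive, not that nothing else could count. That is fair as far as it goes. But it is the only criterion in the plan, and it positively credits a working memory result to Hypothesis 2.
- **Verbal memory could still be analysed.** The clause on other domains allows a RAVLT correlation at the same alpha, and Aim 2(d) itself speaks only of neurocognition. Both points are true. The analysis is not forbidden, but it is labelled secondary or exploratory and is not the test of 2(d). Working memory fits the aim but not the narrower hypothesis.
- **LTP has a method, an outcome and a schedule.** The general sentence on repeated measures ANOVA covers Hypothesis 3, the N100-P200 outcome is defined, and both visits are scheduled. This makes the LTP gap the milder of the two. The general sentence is nevertheless followed by a stated number of models with stated contents, and LTP is in none of them.
- **Coherence is part of the plan.** It is in the schedule, so its presence in model 2 is not foreign. This stands; the problem is the absence of LTP.
- **The count depends on how components are split,** and the drift in 3(c) from memory to cognition is not counted. This stands too. The count is descriptive only.
- **A recall score may not need EEG.** No EEG is recorded during free recall, and the plan does not say whether those who decline EEG still take the RAVLT. This could reduce the cost of the fix; it does not remove the mismatch.

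**Conclusion.** Both mismatches hold. Followed as written, section 9.2 credits a working memory correlation to a verbal memory hypothesis, and it lets 3(b) be called supported without any LTP result. Two of seven lettered components are affected.

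The Synopsis lists EEG outcomes and cognitive performance as secondary endpoints. The primary mGluR5 analyses and the plan's figures are not in question. The point should be fixed, but it does not threaten the study's main conclusion.

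The conclusion assumes that the outcomes and models listed in 9.2 are meant to be the confirming set for each hypothesis. Nothing in the documents suggests otherwise. The 80% uptake figure further assumes the plan's r = 0.55, 30 CUD subjects, and RAVLT data only from those who take the EEG session.

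**What to change.** **2(d), in 9.2.** Choose one of two routes:

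- Name a single RAVLT performance score at Day 0 as the test of 2(d), use it in the correlation and the success rule, and report working memory as secondary. The RAVLT yields learning-trial recall, delayed free recall and recognition, so the score must be fixed in advance. State also whether subjects who decline EEG still take the task.
- If working memory is the intended construct, restate 2(d) accordingly in the Synopsis, 3.1, 9.1 and 9.2.

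**3(b), in 9.2.** Add a repeated measures model of N100-P200 potentiation (post- minus pre-tetanus), Day 28 versus Day 0. Include it in the success rule, and report theta power and LTP separately so that a result on one is not credited to the other.

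**Cost.** The change is wording plus one model on data already planned. Section 1.1 requires IRB approval for any amendment. The RAVLT route may move 2(d) from CogState data due from all CUD subjects to the EEG subset, where at least 24 of 30 are needed by the plan's own figure. The working memory route keeps the full sample but gives up the verbal memory prediction. The LTP model needs EEG at both visits, so its n may fall below 30. It is also a fourth model for Hypothesis 3, and the plan should say how alpha is handled across the four.

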# 6.4 Study Intervention Compliance

CUD subjects will receive motivational enhancement and contingency management (CM) to promote and maintain abstinence. The escalating CM weekly payment schedule for cannabis abstinence is as follows: \$50, \$75, \$125, \$200, \$650 (four-week abstinence bonus). We will collect urine samples to assay THC-COOH principal metabolite of THC. To account for dilution, urinary THC-COOH:creatinine (T:C) ratio will be calculated. Abstinence will be confirmed if the weekly means of urinary T:C ratio decreases over time and does not increase by more than 50% relative to the prior specimen. 113-115

The CUD subjects who drop out (estimated 10%) will be replaced with new CUD subjects to ensure maintenance of adequate statistical power for hypothesis testing. We have accounted for dropouts in the analytic plan, study timeline, and budget.

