information provided in each manuscript, we calculated effect sizes for group differences. Observed effect sizes for group comparisons of cannabis users vs. non-users ranged from d= -0.68 to -1.77, with a median of d=-1.11. These effect sizes are consistent with those observed in our preliminary data, which showed a large effect size associated with differences in mGluR5 availability in CB relative to healthy control individuals in the fronto-limbic circuit (d= 1.72). We will evaluate hypothesis 1 (higher mGluR5 availability in cannabis users) using univariate analysis of variance (ANOVA). Assuming  $\alpha$ =0.05 (two-tailed test) and two groups (cannabis vs. control), our proposed sample size of 60 (30 per group) will provide 81.07% statistical power to detect group differences as small as d= 0.82, which is smaller than the median effect size observed in previous literature and that observed in our preliminary data. Data Analysis for Hypothesis 1: As stated, we will conduct a univariate ANOVA to compare mean fronto-limbic [18F]FPEB  $V_T$  between the HC and cannabis groups. Groups will be carefully matched on demographic variables. However, any demographic variables that differ significantly between groups, including notably age and sex, will be considered for entry as additional fixed factors (categorical variables) or covariates (continuous variables). A significant group difference suggestive of higher mGluR5 availability in CUD subjects will be considered supportive of Hypothesis 1. We will also conduct exploratory analyses to examine betweengroup differences in mGluR5 in other regions, including those involved in affective and cognitive dysregulation (e.g., thalamus, striatum, insula), at the same significance level.

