Aim 3: Within CUD subjects, to determine changes in mGluR5 availability, EEG, and neurocognition following cannabis abstinence. Hypothesis 3: Following cannabis abstinence: (a) mGluR5 will decrease; (b) theta power/LTP will be increased; (c) memory will improve. Power Calculations for Hypothesis 3: Using the same standards applied for Aims 1 and 2, we considered our preliminary data and conducted a literature review to determine the magnitude of effect sizes we might reasonably expect to observe with respect to change in mGluR5, EEG, and cognition as a function of abstinence from cannabis. Values necessary to calculate associated effect sizes were not provided in the reviewed literature. For example, Hirvonen and colleagues (2012) observed a significant increase in CB1 receptor availability in cannabis users after abstinence in both the PFC and amygdala. While percent change (pre-post abstinence) could be roughly estimated from the figure provided, exact values are not available, preventing effect size estimation. We do not have preliminary data examining participants pre- and postcannabis abstinence. However, we believe that comparison of available PET data showing in vivo mGluR5 availability in current cannabis users compared with former users may be indicative of the magnitude of change we can expect to see following abstinence. Comparison of mGluR5 availability in current and former cannabis users in our preliminary sample (n= 5 per group) showed a large effect (d = -1.2). We will evaluate Hypothesis 3 using repeated measures ANOVA. Using a moderate effect size estimate of d = 0.58 at  $\alpha = 0.05$  (highly conservative relative to the noted relevant finding in our preliminary data), a priori power analysis suggested we will require n = 30 to achieve 80.13% power for the planned analysis. Data analysis for Hypothesis 3: To test Hypotheses 3, we will conduct 3 repeated measures ANOVAs to examine changes pre- and post-cannabis abstinence in n = 30 CUD subjects. Specifically, models will evaluate: (1) changes in mGluR5 availability; (2) changes in  $\theta$ -band power and coherence; (3) changes in cognition pre-post abstinence from cannabis in the CUD group. Variables that differ significantly between groups, including age and sex, will be considered for entry into the models. A statistically significant result indicative of lower mGluR5 availability following abstinence (model 1) or higher  $\theta$ - band power and coherence (model 2) and improved cognition (model 3) will be considered supportive of Hypothesis 3.

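### The Aim 3 power statement (n = 30 for 80.13% at d = 0.58) does not reproduce from its stated inputs: the standard paired reading gives 86.7%, and 80% at n = 30 needs an unstated pre-post correlation of about 0.40

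*Combined protocol and SAP*

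**What the plan says.** Section 9.2 (Power Calculations for Hypothesis 3) names the test: "We will evaluate Hypothesis 3 using repeated measures ANOVA". The data are "changes pre- and post-cannabis abstinence in n = 30 CUD subjects", so there is one group and two visits. The effect size is introduced with "Using a moderate effect size estimate of d = 0.58 at" alpha 0.05, and the result is "a priori power analysis suggested we will require n = 30 to achieve 80.13% power for the planned analysis". The passage does not say whether d is scaled by the SD of the change or by the between-person SD, what Day 0 to Day 28 correlation was assumed, or whether the test is one- or two-sided. (Aim 1 is stated as two-tailed.)

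On where 0.58 comes from, the section says that the literature did not supply the values needed for an effect size, and it adds: "We do not have preliminary data examining participants pre- and postcannabis abstinence". It offers a cross-sectional comparison instead: "current and former cannabis users in our preliminary sample (n= 5 per group) showed a large effect", d = -1.2. It calls 0.58 highly conservative relative to that.

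Section 6.4 says that CUD subjects who drop out, estimated at 10%, "will be replaced with new CUD subjects to ensure maintenance of adequate statistical power for hypothesis testing".

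**The concern.** With one group and two visits, the repeated measures ANOVA is a paired t-test. Its power is fixed once n, alpha and the standardised change are given, so the sentence can be checked directly, and it fails the check on the usual reading. The other reading depends on a correlation that the plan neither states nor has data to support.

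This is the only power statement for the within-person comparison, and the Endpoints section makes mGluR5 availability in the using and abstinent states the primary endpoint. As written, a reader cannot tell whether 30 completers is comfortable, just enough, or too few. Comparing 0.58 with -1.2 does not settle this, because a contrast between different people becomes a within-person effect only through that same missing correlation.

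**Working it through.** **Inputs.** From section 9.2, Hypothesis 3: d = 0.58, alpha = 0.05, n = 30, stated power 80.13%, repeated measures ANOVA at two time points. Two-sided is my assumption, because the ANOVA F-test is non-directional. From Hypothesis 1: d = 0.82, two-tailed 0.05, 30 per group, stated power 81.07%. Dropout of 10% is from sections 6.1.1 and 6.4.

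**Step 1. Try to reproduce 80.13%, with d as mean change / SD of change (dz).** Power comes from the noncentral t distribution with df = n - 1 and noncentrality dz × √n. At n = 30 the noncentrality is 0.58 × √30 = 3.177 and the critical value is t(29) = 2.045.

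| n | Power at dz = 0.58, two-sided 0.05 |
|---|---|
| 25 | 79.5% |
| 26 | 81.1% |
| 27 | 82.7% |
| 30 | 86.7% |

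The stated figure is not reproduced at n = 30, and the smallest n reaching 80% is 26. A one-sided test moves further away (92.7% at n = 30). Exactly 80.13% at n = 25 needs d = 0.585. At n = 30, 80.13% corresponds to dz = 0.530.

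**Step 2. Does dropout explain 30?** No. 25/0.9 = 27.8, so 28; 26/0.9 = 28.9, so 29. Dropouts are also replaced, which makes 30 the completer target.

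**Step 3. Try d in raw-SD units.** With equal SDs at the two visits and pre-post correlation ρ, dz = d / √(2(1 - ρ)). At ρ = 0.40, dz = 0.58/√1.2 = 0.529. At ρ = 0.5 the divisor is 1, which returns Step 1. The plan gives no ρ, so a range is shown.

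| ρ (assumed) | dz | Power at n = 30 |
|---|---|---|
| 0 | 0.410 | 58.4% |
| 0.2 | 0.459 | 68.0% |
| 0.3 | 0.490 | 73.7% |
| 0.4 | 0.529 | 80.0% |
| 0.5 | 0.580 | 86.7% |
| 0.6 | 0.648 | 92.9% |
| 0.8 | 0.917 | 99.8% |

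At ρ = 0.40, n = 29 gives 78.6% and n = 30 gives 80.03%, so 30 is then also the minimum. This reading keeps every printed number but supplies one that is not printed.

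**Step 4. Cross-check on Aim 1.** Two independent groups, df = 2n - 2, noncentrality 0.82 × √(n/2). With 30 per group the noncentrality is 3.176 and power is 87.8%. With 25 per group it is 2.899 and power is 81.08%. The stated 81.07% matches 25 per group, and no correlation enters this test.

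**Step 5. The benchmark.** For d = 1.2 in magnitude with 5 per group, t(8) = 1.2 × √2.5 = 1.90, p = 0.094. The 95% interval for d by noncentral t, with the plan's sign, is about -2.5 to +0.2. It includes zero and effects well below 0.58 in magnitude.

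**The case against.** The strongest defence is Step 3. Power for a repeated measures ANOVA normally takes a correlation as an input, and with ρ = 0.40 the printed d, n and power agree to within rounding, with 30 as the minimum n. That defence stands as far as it goes: it shows that the figure could have been obtained properly. It does not show that it was, because the plan gives no correlation and says that it has no pre-post data to supply one.

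Three stronger readings are tempting, and the documents do not support them.

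- A reader might infer that 80.13% is definitely the result for 25 subjects. The Aim 1 match makes a figure carried over from a 25-per-group calculation more likely than coincidence, but no document says so. At the printed d, n = 25 gives 79.5%, and the ρ = 0.40 route remains open.
- A reader might infer that 0.58 was derived from the pilot value of -1.2. It was not. The section discloses the small sample, offers the contrast only as possibly indicative, and uses less than half of it. What is fair to challenge is the description of 0.58 as highly conservative.
- A reader might infer that 27 completers (30 less 10%) already suffice, so replacement is unnecessary. That holds on the dz reading (82.7%), but in raw-SD units 27 completers give 75.4% at ρ = 0.40 and 63.1% at ρ = 0.2. Section 6.4 also justifies replacement by power for hypothesis testing in general, not by this figure.

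It is also fair to say that on the dz reading the sentence understates power, so the sample size is not in danger there.

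**Conclusion.** The statement cannot be reproduced from its inputs and needs correcting. On the standard paired reading, it understates power at n = 30 by 6.5 percentage points (86.65 - 80.13) and overstates the required n by 4 (30 against 26). On the raw-SD reading, it is right only near ρ = 0.40, and power moves by about 40 points across ρ from 0 to 0.8; below about 0.40, n = 30 falls short of 80%. The documents do not say which reading was intended. These results assume a two-sided 0.05 test, one comparison, normal differences and, for the raw-SD scale, equal SDs at the two visits.

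The Aim 1 figure is a firmer mismatch, since no unstated correlation can rescue it: 87.8% at 30 per group against the stated 81.07%. That error is in the safe direction. The benchmark is too imprecise, and of the wrong type, to support the claim that 0.58 is conservative. Nothing here shows that 30 per group is the wrong sample size.

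**What to change.** In section 9.2, Hypothesis 3:

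- Say that the test is two-sided, and define d.
- Replace the power sentence with one on a defined scale, for example: 30 completers give 80% power (paired test, two-sided 0.05) to detect a mean change of 0.53 SD of the change. Add 86.7% at 0.58 only if the original calculation confirms that 0.58 is the SD-of-change effect.
- If 0.58 is in raw-SD units, state the assumed Day 0 to Day 28 correlation, say that it is an assumption, and show power over a range such as the table above.
- Delete the description of 0.58 as highly conservative, or report beside it that d = -1.2 is a between-person contrast of 5 against 5 with a 95% interval of about -2.5 to +0.2.

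In Hypothesis 1, correct the power at d = 0.82 with 30 per group to 87.8%.

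The cost is a wording amendment and a look at the original power output. No participants, visits or analyses are added.
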